8 INVESTIGATIONAL PRODUCTS

Appropriate amount of the Investigational Products will be made available to the investigators organized by B. Braun Melsungen AG (Hospital Care Division). If defects in the Investigational Products are observed, the study manager or the monitor is to be informed.

8.1 Name and Description of the Investigational Product(s)

8.1.1 Qualitative and Quantitative Composition

The following table presents the composition of the Investigational Products, i.e. 1000 mL solution contain each:

	Investigational test regime		Investigational reference regime	
	Gelofusine® Balanced	Sterofundin® ISO	Gelafundin® 4%	Sodium chloride 0.9%
	Isotonic colloidal volume substitute	balanced electrolyte solution	colloidal volume substitute	non-balanced electrolyte solution
Ingredients (1L)				
Gelatine polysuccinate (=modified fluid gelatine)	40.00 g	--	40.00 g	--
Sodium chloride	5.55 g	6.80 g	7.01 g	9.0 g
Sodium acetate trihydrate	3.27 g	3.27 g	--	--
Potassium chloride	0.30 g	0.30 g	--	--
Calcium chloride dehydrate	0.15 g	0.37 g	--	--
Magnesium chloride hexahydrate	0.20 g	0.20 g	--	--
Malic acid	--	0.67 g	--	--
Electrolyte concentrations (1L)				
Sodium	151.0 mmol/L	140.0 mmol/L	153.0 mmol/l	154.0 mmol/L
Chloride	103.0 mmol/L	127.0 mmol/L	120.0 mmol/l	154.0 mmol/L
Potassium	4.0 mmol/L	4.0 mmol/L	--	--
Calcium	1.0 mmol/L	2.5 mmol/L	--	--
Magnesium	1.0 mmol/L	1.0 mmol/L	--	--
Acetate	24.0 mmol/L	24.0 mmol/L	--	--
Malate	--	5.0 mmol/L	--	--
Further characteristics				
pH	7.1 – 7.7	5.1 – 5.9	7.1 – 7.7	4.5 – 7.0
Molecular weight,	30.000 Dalton	--	30.000 Dalton	--

	Investigational test regime		Investigational reference regime	
	Gelofusine® Balanced	Sterofundin® ISO	Gelafundin® 4%	Sodium chloride 0.9%
	Isotonic colloidal volume substitute	balanced electrolyte solution	colloidal volume substitute	non-balanced electrolyte solution
weight average				
Molecular weight, number average	23.200 Dalton	--	23.200 Dalton	--
Theoretical osmolarity	284 mOsm/L	304 mOsm/L	274 mOsm/L	308 mOsm/L

For Gelofusine® Balanced an inhouse-specification applies while all other ingredients are in accordance to the European Pharmacopoeia (Ph. Eur.).

The Investigational Products will be manufactured and released by the Sponsor B. Braun Melsungen AG, Melsungen, Germany (Hospital Care Division) in compliance with Good Manufacturing Practice (GMP). For batch number and expiry date see certificate of analysis.

8.1.2 Pharmaceutical Form

Clear, colourless or slightly yellowish solution for infusion

8.1.3 Nature and Content of Container(s)

Polyethylene plastic bottle (Ecoflac plus®), 500 mL

Ready-to-use container for single use only. The Investigational Products should be administered immediately after connecting the container to the giving set.

8.2 Posology and Method of Administration

8.2.1 Dosage

Administration of the Investigational Products i.e. Gelofusine® Balanced + Sterofundin® ISO or Gelafundin® 4% + Sodium Chloride 0.9% in a blinded manner will be controlled individually by measuring CVP and MAP. The administration will be performed intravenously, starting preoperatively before induction of anesthesia. The following targets and triggers as in clinical routine apply:

The **TARGETS** for volume replacement are defined as:

- Central venous pressure between 10 and 14 mmHg (10 mmHg ≤ CVP ≤ 14 mmHg) minus PEEP after treatment with vasoactive agent

and

- Mean arterial pressure greater than 65 mmHg (MAP > 65 mmHg)

TRIGGERS for infusion of gelatines during surgery and postoperatively are:

- Central venous pressure (CVP) < 10 mm Hg minus PEEP

and

- Mean arterial pressure (MAP) < 65 mm Hg

The crystalloid : colloid ratio is 1 : 1 intra- and postoperatively. The first bottle is the crystalloid followed by the colloid and alternating thereafter. The starting infusion rate of either crystalloid or colloid is 5 mL/kg body weight (broca)/h and will be controlled by using an Infusomat.

The above specifications for crystalloid : colloid ratio and infusion rates are recommendations that ought to be met. However, the rates have to be adjusted according to the individual patient's need as defined by the above targets and triggers, up to a maximum of 5 mL/kg body weight (broca)/h for the crystalloids and of 20 mL/kg body weight (broca)/h for the colloids, as considered necessary by the investigator to stabilize the hemodynamics.

Postoperatively the investigational products will be given according to the patient's need.

8.2.2 Method of Administration

The administration of the Investigational Products is performed intravenously. Do not mix with other medicinal products.

8.2.3 Duration of treatment

Treatment with Investigational Product starts immediately before induction of anesthesia and reliable basal hemodynamic measurements are obtained and before skin incision.

After final positioning of the patient in the operation theatre basal hemodynamic measurements will be recorded. Prior to induction of anesthesia the Investigational Product will be given according to the above described dosage (see 8.2.1).

Treatment with Investigational Product ends 12 hours after end of surgery.

Thereafter volume replacement will be performed at the discretion of the attending physician.

8.3 Labelling

The labels were designed in accordance with GMP annex 13 and will contain the information as required by the pertinent national requirements. They must remain attached to the containers and the boxes for the duration of the clinical trial and should not be defaced.

Examples of the intended labels on the primary and secondary containers are given below. The layout and addresses may be subject to change. Variable data is indicated with "x" as placeholders.

The bottles with odd numbers contain always the crystalloid component of the respective regimen and the bottles with even numbers always the colloid component. In addition the labels of the crystalloid and colloid component will have a different colour.

Nur zur klinischen Prüfung bestimmt
 
Studien-Nr.: HC-G-H-0904 EudraCT-Nr: 2010-018524-58
 
500 ml Infusionslösung zur intravenösen Anwendung
 
1) Patienten-Nr. xxx 2) Flaschen-Nr. xx
 
Flaschen nur in aufsteigender Reihenfolge verwenden!
 
Hauptprüfarzt:
	
Anwendung und Dosierung gemäß Studienprotokoll
 
Nur zu verwenden, wenn die Flasche unverletzt ist und Lösung klar und frei von sichtbaren Partikeln ist. Zur einmaligen Anwendung bestimmt. Nach einem Anwendungsgang sind eventuell nicht verbrauchte Restmengen der Lösung zu verwerfen. Flasche nach der Behandlung im Patientenkarton aufzubewahren.
 
Nicht über 25°C lagern. Nicht im Kühlschrank lagern oder einfrieren.
 
Code-Nummer: xxxxxxxx/xxxxxxx_x Verwendbar bis xx/xxxx
 
Sponsor: B. Braun Melsungen AG [name]

---	---

Nur zur klinischen Prüfung bestimmt
 
Studien-Nr.: HC-G-H-0904 EudraCT-Nr: 2010-018524-58
 
500 ml Infusionslösung zur intravenösen Anwendung
 
1) Patienten-Nr. xxx 2) Flaschen-Nr. xx
 
Flaschen nur in aufsteigender Reihenfolge verwenden!
 
Hauptprüfarzt:
	
Anwendung und Dosierung gemäß Studienprotokoll
 
Nur zu verwenden, wenn die Flasche unverletzt ist und die Lösung klar und frei von sichtbaren Partikeln ist. Zur einmaligen Anwendung bestimmt. Nach einem Anwendungsgang sind eventuell nicht verbrauchte Restmengen der Lösung zu verwerfen. Flasche nach der Behandlung im Patientenkarton aufzubewahren.
 
Nicht unter 10°C und nicht über 25°C lagern. Nicht einfrieren.
 
Code-Nummer: xxxxxxxx/xxxxxxx_x Verwendbar bis xx/xxxx
 
Sponsor: B. Braun Melsungen AG [name]

---	---

The labels for the secondary containers are:


Nur zur klinischen Prüfung bestimmt Studien-Nr.: HC-G-H-0904 EudraCT-Nr.: 2010-018524-58
 
13 Flaschen 500 ml Infusionslösung zur intravenösen Anwendung
 
Patienten-Nr.: xxx
 
Flaschen nur in aufsteigender Reihenfolge verwenden!
 
Hauptprüfarzt:
	
Anwendung und Dosierung gemäß Studienprotokoll
 
Nur zu verwenden, wenn der Patientenkarton vor der Entnahme der ersten Flasche ungeöffnet ist, die Flaschen unverletzt sind und die Lösungen klar und frei von sichtbaren Partikeln sind. Zur einmaligen Anwendung bestimmt. Nach einem Anwendungsgang sind eventuell nicht verbrauchte Restmengen der Lösung zu verwerfen. Nach der Behandlung ist der Patientenkarton mit den leeren, geöffneten und ungeöffneten Flaschen aufzubewahren.
 
Nicht über 25°C lagern. Nicht im Kühlschrank lagern oder einfrieren.
 
Code-Nummer: xxxxxxxx/xxxxxxx_x Verwendbar bis xx/xxxx
 
Sponsor: B. Braun Melsungen AG [name]

--	--

Nur zur klinischen Prüfung bestimmt Studien-Nr.: HC-G-H-0904 EudraCT-Nr.: 2010-018524-58
 
13 Flaschen 500 ml Infusionslösung zur intravenösen Anwendung
 
Patienten-Nr.: xxx
 
Flaschen nur in aufsteigender Reihenfolge verwenden!
 
Hauptprüfarzt:
	
Anwendung und Dosierung gemäß Studienprotokoll
 
Nur zu verwenden, wenn der Patientenkarton vor der Entnahme der ersten Flasche ungeöffnet ist, die Flaschen unverletzt sind und die Lösungen klar und frei von sichtbaren Partikeln sind. Zur einmaligen Anwendung bestimmt. Nach einem Anwendungsgang sind eventuell nicht verbrauchte Restmengen der Lösung zu verwerfen. Nach der Behandlung ist der Patientenkarton mit den leeren, geöffneten und ungeöffneten Flaschen aufzubewahren.
 
Nicht unter 10°C und nicht über 25°C lagern. Nicht einfrieren.
 
Code-Nummer: xxxxxxxx/xxxxxxx_x Verwendbar bis xx/xxxx
 
Sponsor: B. Braun Melsungen AG [name]

--	--

Further principal investigator (Hauptprüfarzt) to be mentioned on the respective labels:

Study site 'Frankfurt/Main':

8.4 Packaging

The investigational products will be packed per patient with a special label on the boxes indicating for which patient of the study the samples are. The boxes contain 26 bottles per patient (i.e. 13 bottles of the colloid and crystalloid component respectively) and cover the whole study period.

The investigational products (colloid and crystalloid component) will be made available in the following type of packaging and content:

- Polythene plastic bottle (Ecoflac plus) – Colloid and crystalloid component
- 2 boxes x 13 bottles x 500 mL

8.5 Storage

The storage of the investigational products will be at a safely locked place with limited access only to authorized staff. All investigational products of the colloid component are not to be stored below 10°C and not above 25°C. The investigational products of the crystalloid component are not to be stored above 25°C and not in the fridge.

Do not freeze.

8.6 Investigational Product Accountability

In accordance with regulations, the pharmacist or other appropriate individual, who is designated by the Investigator, will keep an inventory of all clinical trial material (CTM) received. All used and unused CTM must be accounted for on an Inventory Form which will be provided to the pharmacist or other designated individual by the Site Monitor. CTM inventory forms will be examined and reconciled by the Investigator at the end of the study.

These records should include dates, quantities, batch / serial numbers, expiration dates (if applicable), and - if applicable - the unique code numbers assigned to the Investigational Product(s) and study patients. Investigators should maintain records that document adequately that the patients were provided the doses / treatments specified by the protocol.

After Investigational Product administration, i.e. 12 hours after end of surgery, all unused/opened/unopened bottles must be returned for product accountability.

A copy of the completed Inventory Form must be retained in the Investigator's study files, and a copy must be filed in the Sponsor Trial Master File.

8.7 Destruction / Retrieval of Surplus Investigational Products

Used and opened as well as surplus investigational products are to be returned to the study pharmacy after termination of the entire study. The Sponsor is responsible for the destruction of them.

9 CONCOMITANT THERAPY

Necessary concomitant medication pre-anesthesia – Patient`s standard medication

- Placement of intravenous and other catheters necessary for the infusion of the investigational products and for monitoring purposes
- Performance of hemodynamic examinations and the obtainment of blood samples for laboratory measurements (see 10)
- Medication as clinically required

Necessary concomitant medication during anesthesia and abdominal surgery:

- Noradrenalin as vasoactive treatment
- Medication as clinically required (e.g. inotropic drugs according to the medical opinion)
- Anesthesia will follow a standardized protocol of a balanced anesthesia using Sevoflurane as volatile anesthetic in combination with a peridural anesthesia where the opioid is arbitrary (left to the standard operating procedure of the study centers):
 - Thoracic peridural catheter (starting with 0.75% Naropin, followed by a mixture of Naropin 0.16% and Sufentanil 0.5 µg/mL using an infusion pump)
 - Anesthesia induction: 1 – 2 mg/kg/BW Propofol
1 – 5 µg/kg/BW Fentanyl
0.5 – 0.6 mg/kg/BW Rocuronium
 - Anesthesia maintenance: Sevofluran

Necessary concomitant therapy during anesthesia and abdominal surgery:

- Ventilation which is aimed at a CO₂ between 38 and 42 mmHg

Volume replacement:

- Administration of investigational products according to the **targets** and **triggers** (see 8.2)
- Administration of blood products according to the following triggers:

Trigger for administration of red blood cells (RBCs) are:

- Hemoglobin (Hb) ≤ 6 g/dL
- Hemoglobin 6 – 8 g/dL, in case of restricted compensation (e.g. coronary heart diseases, cardiac insufficiency and cerebrovascular insufficiency) and / or anemic hypoxia (e.g. tahcaycardia, hyopotension, ischemia and lactatacidose)

Trigger for administration of fresh frozen plasma are:

- Bleeding or
- aPTT > 60s or
- fibrinogen < 2g/dL

Trigger for administration of platelets are:

- Bleeding or
- platelet count < 50.000/ μ L

Unauthorized concomitant medication:

- Administration of other colloid or crystalloid volume replacement agents (e.g. other gelatine solutions, albumin, dextran, HES solutions, other crystalloid solutions) aside from investigational products, with exception of concentrated electrolytes for individual corrections
- Administration of sodium bicarbonate

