	
The TRIGGERS for volume replacement are defined as:
 
 ▪ Central venous pressure is <10 mmHg (CVP <10 mmHg) minus PEEP 
and
 
 ▪ Mean arterial pressure is <65 mmHg (MAP < 65 mmHg) 
Postoperatively the investigational products will be given according to the patient's need.
 
Trigger for administration of blood products are:
 
Red blood cells (RBCs):
 
Hemoglobin (Hb) \leq 6 g/dL
 
Hemoglobin 6 – 8 g/dL, in case of restricted compensation (e.g. coronary heart diseases, cardiac insufficiency and cerebrovascular insufficiency) and / or anemic hypoxia (e.g. tachycardia, hypotension, ischemia and lactatacidosis)
 
Fresh frozen plasma (FFP):
 
Bleeding or aPTT > 60s or fibrinogen < 2g/dL
 
Platelets:
 
In case of bleeding or platelet count < 50.000/μL
 
Other blood products (e.g. fibrinogen, thrombocyte concentrate) according to the decision of the attending physician
 
The investigational products will be applied in a blinded manner.
 
Treatment Duration
 
Treatment with the investigational products will start immediately before induction of anesthesia. It will be given intraoperatively until 12 hours after end of surgery.
 
After investigational product treatment the choice of need volume replacement is at the discretion of the attending physician.

Visit Schedule
	
Pre-operatively
 
 ▪ verification of inclusion and exclusion criteria including informed consent ▪ pre-operative blood sampling for laboratory measurements ▪ pregnancy test in urine for women of childbearing potential ▪ history, demographics ▪ Apfel-Score ▪ pre-operative medication / therapy

Pre-anesthesia

- randomization
- baseline recording of hemodynamics
- blood sampling for baseline laboratory
- baseline ROTEM and baseline platelet aggregation
- set of catheters (e.g. arterial / central venous catheter)
- administration of first crystalloid bag
- drug monitoring and tolerance
- induction of anesthesia
- concomitant medication and therapy
- adverse events/ reactions

After induction of anesthesia / prior surgery

- administration of investigational products
- time on ventilator
- final positioning of patient in operation theatre
- set of urinary catheter
- hemodynamics
- laboratory measurements
- drug monitoring and tolerance
- concomitant medication and therapy
- adverse events/ reactions

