7.3 Patient Exclusion Criteria

Patients will not be considered for participation in the study if any of the following criteria listed below apply:

- Patients of ASA-class $> III$
- Patients suffering from known hypersensitivity to gelatine or to any of the constituents of the gelofusine solutions
- Patients treated with other colloid solutions and / or blood products 24 hours prior to surgery
- Patients on hemodialysis
- Patients suffering from decompensated renal function (i.e. serum creatinine > 3.0 mg/dL)
- Patients suffering from

- Hypervolemia
 - Hyperhydration
 - Severe blood coagulation disorders
 - Hyponatremia (serum(Na⁺) < 130 mmol/L)
 - Hyperchloremia (serum(Cl⁻) > 110 mmol/L)
 - Hypercalcaemia (serum(Ca⁺⁺ - total) > 3 mmol/L or serum (Ca⁺⁺-free) > 1.5 mmol/L)
 - Metabolic alkalosis
 - Severe heart insufficiency
 - Severe generalized edema
 - Intracranial haemorrhage
 - Hyperkalaemia (serum(K⁺) > 5.5 mmol/L)
 - Estimated perioperative need for blood products of more than 3.5 mL/kg body weight (Broca)
 - Lactation period
 - Simultaneous participation in another clinical trial
 - Emergencies
 - Patients suffering from
 - moderate heart or lung insufficiency
 - moderate lung edema
 - hypertonia
 - eclampsia
- who do not allow the IP regimen as required.

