10.2 Secondary Variables

10.2.1 Secondary Variables – Safety

Laboratory:

The analysis of blood and urine samples will be performed by the hospital laboratories according to the corresponding methods and guidelines (see Appendix 3). The reference ranges of these parameters are given in Appendix 4.

Blood samples for laboratory parameters will be taken, if not stated otherwise, at least:

- baseline i.e. prior to induction of anesthesia
- admission to ICU / IMC
- 6 hours after end of surgery
- 12 hours after end of surgery

Additional times will be listed in the context of the respective parameter.

The results of all blood analyses performed after blood sampling will be documented as follows:

- date and time of blood sampling [dd.mm.yyyy / hh:mm].

Arterial blood gas analyses

- pondus hydrogenii (pH); not temperature corrected.
- Base excess (BE) [mmol/L]
- Bicarbonate (HCO_3) [mmol/L]
- Lactate [mmol/L]
- Sodium (Na^+) [mmol/L]
- Potassium (K^+) [mmol/L]
- Calcium (Ca^{2+}) [mmol/L]
- Chloride (Cl^-) [mmol/L]
- Partial pressure of carbon dioxide (pCO_2) [mmHg]
- Partial pressure of oxygen (pO_2) [mmHg]
- Oxygen saturation (SaO_2) [%]
- Hemoglobin (Hb) [g/dL]
- Hematocrit (Hct) [%]

Hemoglobin acts as trigger for the administration of the blood products and will be monitored intraoperatively.

Additionally to the above mentioned measurements blood samples for arterial blood gas analysis will be taken intraoperatively every 15 min including recovery room every 60 minutes and additional measurements depending on the investigators decision.

Coagulation status

- Antithrombin III (AT III) [%]
- Fibrinogen [g/dL]
- Platelet count [μL]
- Activated partial thromboplastin time (aPTT) [s]

Fibrinogen, activated partial thromboplastin time (PTT), and platelet count act as trigger for the administration of the blood products and will be monitored intraoperatively.

These parameters will be recorded at baseline, at admission ICU /IMC, 6 hours and 12 hours after end of surgery.

- ROTEM (CT, MCF, LI 30)
- Platelet aggregation (TRAPtest, ASPItest, ADPtest) – only site Frankfurt am Main

These parameters will be recorded at baseline, at admission ICU /IMC, 6 hours and 12 hours after end of surgery.

Renal function

Blood samples:

- Serum creatinine (SCrea) [mg/g]
- Creatinine clearance [mL/min]
- Blood urea nitrogen (BUN) [mg/dL]
- Cystatin C [mg/L]

GFR and creatinine clearance will be calculated according to the Cockcroft-Gault Formula (see Chapter 14.1.1)

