12.2 Tabular Overview

PROCEDURE	TIME								
	Pre-operative	Randomization	Prior to induction of anesthesia	After induction of anesthesia	During surgery	End of surgery	Admission to ICU / IMC	6 hours after end of surgery	12 hours after end of surgery / ICU/IMC discharge (which occurs latest)
Inclusion / exclusion criteria	x								
Written informed consent	x								
Pregnancy test (woman)	x								
History, demographics, Apfel-Score	x								
pre-operative medication	x								
Randomization		x							
Surgery related data					x	x			
Time on ventilator				x	x	x	x	x	x
Ventilator settings				x	x	x	x	x	x
Set of catheters and final positioning of patient			x	x					
Infusion of the investigational test or reference products			continuously ^h						
Hemodynamics			x ^a	continuously ^e					
Drug monitoring and tolerance			continuously						
Drainage blood losses and estimated blood loss					x	x			
Set of urinary catheter			x						
Recording of							continuously		

TIME	Pre-operative	Randomization	Prior to induction of anesthesia	After induction of anesthesia	During surgery	End of surgery	Admission to ICU / IMC	6 hours after end of surgery	12 hours after end of surgery / ICU/IMC discharge (which occurs latest)
PROCEDURE									
secondary bleeding									
Laboratory (blood and / or urine sampling)			x ^a	x ^b	x ^b	x ^b	x	x	x ^g
Blood gas analysis			x	x ^f	x ^f	x ^f	x	x	x ^g
Coagulation			x				x	x	x ^g
ROTEM			x				x	x	x ^g
Platelet aggregation (only site Frankfurt / Main)			x				x	x	x ^g
Renal function			x				x		x ^g
(Serious) adverse events / reactions			continuously						
Concomitant medication incl. blood products			continuously						
Diuresis						x ^c			x ^d
Length of ICU / IMC stay									x ⁱ
Study termination									x ^d

a baseline

b Hb, aPTT, fibrinogen and PC serve as trigger for blood product-administration; blood gas analysis intraoperatively every 15 min including recovery room every hour

c cumulated diuresis from start of anesthesia until end of surgery

d cumulated diuresis from end of surgery until 12 hours after end of surgery or ICU/IMC discharge, which occurs latest

e intraoperative every 15 min; CVP minus PEEP and MAP serve as trigger for IP-administration

f intraoperative every 15 min, recovery room hourly

g 12 hours after end of surgery

h until 12 hours after end of surgery

i discharge from ICU / IMC

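### The fibrinogen limit for giving fresh frozen plasma is written in g/dL, which sets it at 20 g/L, a level that essentially every patient is below

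*Protocol*

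**What the plan says.** The synopsis gives the rule for fresh frozen plasma on one line: "Bleeding or aPTT > 60s or fibrinogen < 2g/dL". Section 9 (Concomitant therapy) repeats the three criteria as a list, also joined by 'or', with the last one again "fibrinogen < 2g/dL". A fibrinogen result alone is therefore enough to call for plasma.

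Fibrinogen is meant to be used in this way. Section 10.2.1 says of fibrinogen, aPTT and platelet count that they "act as trigger for the administration of the blood products and will be monitored intraoperatively". Footnote b to the schedule in section 12.2 agrees: "Hb, aPTT, fibrinogen and PC serve as trigger for blood product-administration". In its list of coagulation variables, section 10.2.1 records fibrinogen in g/dL, and among the details to be documented for each blood product it names fibrinogen as an example of a reason for giving it.

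The text shown does not state the limit in another unit, correct it or give a fibrinogen range. For ranges, section 10.2.1 points elsewhere: "The reference ranges of these parameters are given in Appendix 4".

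**The concern.** A transfusion trigger has to separate patients who need the product from those who do not. A limit of 2 in g/dL is 20 g/L, far above any fibrinogen level one would expect in a surgical patient. Because the criteria are alternatives, the plasma rule as written is met whatever the bleeding status or the aPTT.

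Two consequences follow, depending on how sites react:

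- **The rule is followed literally.** Patients receive plasma that they do not need between baseline and the end of surgery. That is the interval over which the change in base excess and chloride, the primary variables, is measured. It also sits badly with section 7.3, which excludes patients whose expected need for blood products exceeds 3.5 mL/kg.
- **Sites silently use a limit of their own.** The two centres may then choose different ones. The recorded reason for giving plasma would no longer correspond to the protocol, and requirement of blood products is a secondary safety variable.

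**Working it through.** The protocol gives no derived figure to reproduce here. The check is a unit conversion followed by a comparison with plausible fibrinogen levels.

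**Inputs**

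- Limit: 2 g/dL (synopsis; section 9).
- Fibrinogen levels: not in the text shown. *Assumption:* 1.5 to 4.5 g/L as a usual adult range, and 10 g/L as an extreme acute-phase value.
- For the share of patients below the limit. *Assumption:* normal distributions with mean/SD of 3/0.6, 4/1.0, 5/1.5 and 7/2.0 g/L, which run from ordinary to clearly raised levels.

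**Step 1: conversion**

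- 2 g/dL × 10 dL/L = 20 g/L
- 2 g/dL × 1000 mg/g = 2000 mg/dL

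**Step 2: limit relative to assumed patient values**

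- Upper end of the usual range: 20 / 4.5 = 4.4
- Lower end of the usual range: 20 / 1.5 = 13.3
- Extreme value: 20 / 10 = 2.0

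Even the extreme patient is at half the limit.

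**Step 3: share of patients below the limit**, Φ((limit − mean) / SD), for the written limit and for one ten times lower (20 / 10 = 2 g/L = 0.2 g/dL = 200 mg/dL):

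| Assumed mean / SD (g/L) | Below 20 g/L (as written) | Below 2 g/L |
|---|---|---|
| 3 / 0.6 | effectively 100% | 4.8% |
| 4 / 1.0 | effectively 100% | 2.3% |
| 5 / 1.5 | effectively 100% | 2.3% |
| 7 / 2.0 | more than 99.99999999% | 0.6% |

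For the last row, (20 − 7) / 2.0 = 6.5 standard deviations and (2 − 7) / 2.0 = −2.5 standard deviations.

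At 20 g/L the criterion is met by everyone under each assumption. At 2 g/L it is met by about 0.6% to 5%, and 2 lies inside the assumed usual range (1.5 < 2 < 4.5), so the criterion would separate patients.

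**Step 4: could it be a text-extraction fault?** The same number and unit stand in both the synopsis and section 9, and section 10.2.1 separately lists fibrinogen in g/dL. A reading error is unlikely. The recording unit is valid in itself; the error is the value 2 in that unit. Using g/dL on the record also makes a literal reading easier: a result entered as 0.3 is plainly below 2.

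**The case against.** The best defence is that this is an obvious slip with little practical effect. An anesthetist who sees a normal laboratory result will not give plasma because of this line, and will probably read it as 2 g/L. Excluding patients with a high expected need for blood products shows that plasma for all was never intended. Section 10.2.1 has other loose unit labels, such as mg/g for serum creatinine, which suggests careless editing and not a chosen rule. All of this is fair and limits the likely harm. But a rule that staff must disregard in order to act safely is not a usable instruction.

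The second argument is that correcting the number does not make the whole trigger selective, because unqualified bleeding is also sufficient and blood loss is routinely recorded in these operations. This stands as a limit on what the fix achieves: it restores the fibrinogen criterion only.

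The third is that the consequences for the trial are not quantified. This too stands. No size is given for any effect of plasma on base excess or chloride. Randomization is stratified by centre and site enters the primary analysis as a covariate, so differing local practice should be roughly balanced across arms. Tests of secondary variables are exploratory. These points argue against calling this a threat to the primary comparison, and no such claim is made.

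Finally, the patient range is assumed and the intended value of 2 g/L is inferred. The first hardly matters, since the limit is twice even the extreme assumed value. The second is why the clinical team must confirm the value.

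**Conclusion.** The concern holds. As written, the fibrinogen criterion for fresh frozen plasma is 20 g/L, probably ten times the intended limit, and essentially every patient meets it throughout surgery. The conclusion rests on the assumed fibrinogen range but is insensitive to it: a patient would need more than 20 g/L to escape the trigger.

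This is a wrong decision threshold in a treatment rule, stated in the protocol itself. It should be corrected because it concerns unneeded plasma and the consistency of a secondary safety variable between centres. It does not bias the comparison of arms, and no effect on the primary endpoints has been sized. Confidence is high in the arithmetic and in the literal error, and lower as to how much would change in practice.

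**What to change.** - In the synopsis and in section 9, replace the limit, most plausibly with fibrinogen < 2 g/L (= 0.2 g/dL = 200 mg/dL). The clinical team should first confirm the value against the laboratory reference ranges in Appendix 4.
- In section 10.2.1, record fibrinogen in the unit used for the trigger, so that the recorded result and the limit can be compared directly.

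The cost is a wording correction in two places plus, if g/L or mg/dL is chosen, one change of recording unit. Sample size and analysis do not change.
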